- **DLT Period:** A 5-week (Arm A) or 12-week (Arm B) DLT period after the first dose of M3814 for the evaluation of 'acute' systemic and local toxicity in all subjects in Phase Ia, and a 12-week DLT period after the first dose of M3814 in the first 3 subjects of the safety run-in part in the NSCLC expansion cohort during Phase Ib (Arm A)

- **Short-term Safety Follow-up:** A follow-up period of 30 days after the end of RT for evaluation of safety
- **Mid-term Safety Follow-up:** A safety follow-up period of 3 months after the end of RT to evaluate late signs of RT-induced toxicity on normal surrounding tissues
- **Long-term Safety Follow-up:** A safety follow-up period until 12 months after end of RT to evaluate late signs of RT-induced toxicity on normal surrounding tissues
- **Survival Follow-up:** A follow-up period that will continue until 12 months after the last subject has stopped RT/CRT.

Ancillary cPoP part of the trial

A follow-up period of 30 days after the end of the RT/M3814 for evaluation of safety. Subjects will be permitted to receive any indicated therapeutic modality as soon as clinically indicated after Day 10.

Dose escalation

M3814 dose escalation will not proceed to the next dose level until all subjects have completed the DLT period.

Phase Ia

A Bayesian two-parameter logistic regression model with overdose control will be used to assist the SMC with dose selection during the Phase Ia dose escalation. Cohorts of 3 subjects each will be treated at the same dose level (capsule starting dose: 100 mg QD for Arm A and 50 mg QD for Arm B). The model incorporates prior information (from nonclinical data) and observed information from each completed cohort (and data from all previous cohorts) to provide a recommended dose for the next cohort. A preselected set of acceptable doses are considered by the model, however doses which are not part of the prespecified set may be chosen as well. The model ensures that recommended doses correspond to a probability of less than 25% that the true DLT rate is more than 35% in Arm A and 45% in Arm B. Dose escalation will stop in each arm as soon as the first of the following stopping rules apply: a maximum of 30 subjects are included, more than three cohorts are assigned to the same dose level, or the estimate of DLT probability at the MTD reaches a sufficient precision.

Phase Ib

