RT: 10-25 Gy ^a		Lesion 1	Lesion 2		
Trial Visit Day	-21 to -1	1 ^b	2	10	32
Visit window (days)	-	-	-	±1	±2
12-lead ECG (including QTcF)	X				
CCI					
PK blood sample			X ^m		
CCI					
Local tumor assessment (RECIST) ^{o, p}	X			X	

ECG = electrocardiogram; ECOG PS = Eastern Cooperative Oncology Group performance status; FU = follow-up; F/W= fraction per week; Gy = Gray; HIV = human immunodeficiency virus; L1 = Lesion 1; L2 = Lesion 2; PD = pharmacodynamics; PK = pharmacokinetics; QTcF = Fridericia-corrected QT interval; RECIST = Response Evaluation Criteria in Solid Tumors; RT = radiotherapy.

- To be given 1.5 hours (± 30 minutes) after dosing.
- For logistical reasons (handling and sending materials), Day 1 must be on a Wednesday or earlier.
- Hepatitis B and C testing to be performed at Screening unless obtained within 3 months prior to Screening. Screening for HIV will be performed according to local practice and local regulatory guidance.
- Heart rate, diastolic and systolic blood pressure, body temperature, and body weight.
- Height measured at Screening only.
- Predose vital signs.
- Local tolerability only.
- See [Table 15](#) for details of hematology tests.
- See [Table 15](#) for details of serum chemistry tests.
- Urinalysis: dipstick followed by microscopic examination if abnormal results.

CCI

m. PK samples will be collected as described in [Table 9](#). Sampling schedule may be changed in the course of the trial.

CCI

- o. Local tumor assessment (in irradiated lesions) by clinical exam or imaging according to RECIST v1.1. Baseline tumor evaluation can be up to 21 days old when treatment starts.
- p. Only applicable for additional cohorts with M3814 CCI [REDACTED] formulation.

Table 8 Radiotherapy (Alone) and M3814 + RT Schedule for the Ancillary Clinical Proof-of-Principle (cPoP) Part of the Trial

		Day 1 (baseline) ^a	Day 1	Day 2
Lesion 1	Biopsy	B1	B3 ^b	--
	RT^c	--	+	--
	M3814	--	-	--
Lesion 2	Biopsy	B2	--	B4 ^b
	RT^c	--	--	+
	M3814	--	--	+

RT = radiotherapy.

- a. Baseline biopsy to be taken any time prior to RT for both lesions (Screening to Day 1).
- b. Core biopsy needs to be performed 2 to 4 hours after RT. Detailed time schedule and sample collection procedures will be described in the laboratory manual.
- c. Radiotherapy will be given as a single high dose of RT (10-25 Gy). The dose of M3814 should be administered 1.5 hours (\pm 30 minutes) before radiotherapy.

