Known and Potential Risks and Benefits to Human Subjects

This clinical trial will be conducted in compliance with the ICH E6 GCP Guidance, and any additional applicable regulatory requirements.

The benefit-risk relationship has been carefully considered in the planning of the trial. Based on the CCI data on M3814 and on published nonclinical and clinical data showing evidence of cell death and tumor shrinkage after single-agent use in tumors with pre-existing altered repair mechanisms, thus illustrating the concept of synthetic lethality, the conduct of this trial is considered justifiable using the dose(s) and dosage regimen(s) of the IMP as specified in this clinical trial protocol [1, 2, 3].

It is known that RT can cause acute toxicities in the form of, for example, radiation dermatitis and mucositis. Definitive concurrent CRT, considered the SoC for inoperable locoregionally advanced SCCHN, is associated with significant acute toxicities including stomatitis (oral mucositis), swallowing dysfunction (odynophagia, dysphagia), decreased appetite, and dermatitis [4, 5, 6, 7]. For incurable head and neck cancers, RT has been demonstrated to be an effective palliative modality and most acute toxicities are generally related to mucosal inflammation and dermatitis, even though the severity and frequency of these AEs were lower compared with CRT in the curative setting [8]. Late toxicities arising 3 months or later after the end of RT can be seen in the form of, for example, xerostomia, esophagitis, pneumonitis, and fibrosis. Patients should be

reminded to contact the trial site immediately in case of toxicities where they will be evaluated and treated as appropriate according to institutional guidelines. Potentially acute and late toxicities can be more severe when RT is given in combination with M3814. This will be evaluated on an ongoing basis for up to 12 months after the end of treatment.

In this trial, the SMC will monitor the benefit-risk ratio on an ongoing basis. The trial will be discontinued in the event of any new findings that indicate a relevant deterioration of the benefit-risk ratio for the subjects, which would render continuation of the trial unjustifiable.

Based on the available **CCI** and clinical data to date, the conduct of the trial specified in this protocol is considered justifiable in subjects with locally advanced disease.

4 Trial Objectives

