Subject overall safety will be evaluated up to Day 10 (Follow-up Period). Local tolerability will be reported on Days 10 and 32 (Days 8 and 30 after the end of treatment, Safety Follow-up Period). In addition, on Day 10 local tumor response will be assessed in irradiated lesions (only applicable for additional cohorts of M3814 [CC1] formulation). Subjects will be permitted to receive any indicated systemic therapeutic modality as soon as clinically indicated after Day 10.

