7.1.3.7 Follow-up for the Ancillary cPoP Part of the Trial

The following assessments will be performed on Day 10 and Day 32 (8 and 30 days after end of treatment):

- Assessment of vital signs (blood pressure, heart rate, and body temperature), body weight (Day 10 only)
- Evaluation of all tissues in RT area
- Assessment of AEs (local tolerability 30 days after last trial drug administration)
- Documentation of concomitant medications (only at Day 10)
- Safety laboratory (hematology, serum chemistry and coagulation)
- Local tumor assessment (in irradiated lesions) by clinical exam or imaging according to RECIST v1.1 (only at Day 10 and only applicable for additional cohorts of M3814 [CC1 formulation]).

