7.4 Assessment of Safety

The safety profile of M3814 will be assessed through the recording, reporting and analysis of baseline medical conditions, AEs, physical examination findings including vital signs and monitoring for bleeding, laboratory tests, ECOG PS, and 12-lead ECGs.

Comprehensive assessment of any apparent toxicity experienced by each subject will be performed from the time of giving informed consent up to 12 months after RT completion. The Investigator will report any AEs, whether observed by the Investigator or reported by the subject (see Section [7.4.1.2](#)). The reporting period for AEs is described in Section [7.4.1.3](#).

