7.4.1.3 Definition of the Adverse Event Reporting Period

The AE reporting period for safety surveillance begins when the subject is initially included in the trial (date of first signature of informed consent) and continues through the trial's post-treatment follow-up period up to PTD 365.

A TEAE is defined as any AE that occurs from the day of first dose of M3814 (regardless of pretreatment or post-treatment on first dosing day), through Day 30 after the end of RT.

Any SAE assessed as related to M3814 must be reported whenever it occurs irrespective of the time elapsed since the last administration of M3814.

7.4.1.4 Procedure for Reporting Serious Adverse Events, Adverse Events of Special Interest and Dose Limiting Toxicities

Serious Adverse Events

In the event of any new SAE occurring during the reporting period, the Investigator must immediately (within a maximum of 24 hours after becoming aware of the event) inform the Sponsor or its designee in writing. All written reports should be transmitted using the SAE Report Form, which must be completed by the Investigator following specific completion instructions.

In exceptional circumstances, an SAE (or follow-up information) may be reported by telephone; in these cases, a written report must be sent immediately thereafter.

Relevant pages from the eCRF may be provided in parallel (e.g., medical history, concomitant medication). Additional documents may be provided by the Investigator, if available (for example, laboratory results, hospital report and autopsy report). In all cases, the information provided on the SAE Report Form must be consistent with the data about the event recorded in the eCRF.

The Investigator must respond to any request for follow-up information (e.g., additional information, outcome, final evaluation, other records where needed) or to any question the Sponsor/designee may have on the AE within the same timelines as those noted above for initial reports. This is necessary to ensure prompt assessment of the event by the Sponsor or designee and (as applicable) to allow the Sponsor to meet strict regulatory timelines associated with expedited safety reporting obligations.

Requests for follow-up will usually be made via the responsible Monitor, although in exceptional circumstances the CRO's Global Drug Safety department may contact the Investigator directly to obtain further information or to discuss the event.

Dose Limiting Toxicities

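### In the cPoP part, systemic adverse events and concomitant medication are recorded only to Day 10, but the protocol's TEAE window runs to Day 32

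*Protocol*

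**What the plan says.** The text specific to cPoP sets a short and partly local safety follow-up:

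- Section 5.1 (Follow-up Periods, ancillary cPoP part): "Subject overall safety will be evaluated up to Day 10 (Follow-up Period"), and then "Local tolerability will be reported on Days 10 and 32 (Days 8 and 30 after the end of treatment, Safety Follow-up Period"). It also lets subjects start other systemic therapy after Day 10 when clinically indicated.
- Table 7, footnote to the Day 32 adverse event assessment: "Local tolerability only".
- Section 7.1.3.7 repeats the restriction to local tolerability at 30 days and adds "Documentation of concomitant medications (only at Day 10"). It still schedules hematology, serum chemistry and coagulation at both Day 10 and Day 32.

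The general text sets a wider frame, with no cPoP exception:

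- Synopsis, cPoP follow-up: "A follow-up period of 30 days after the end of the RT/M3814 for evaluation of safety".
- Section 7.4.1.3: TEAEs run from the day of the first M3814 dose through 30 days after the end of RT, and adverse event reporting "continues through the trial's post-treatment follow-up period up to PTD 365".
- Section 8.5.4.1: TEAEs are tabulated until 30 days from the end of treatment.
- Section 7.4.1.2: the subject is asked about changes at every trial visit, and any unfavorable change in the reporting period is recorded.
- Section 6.6: all concomitant medication taken during the trial is recorded.
- Section 7.4: "Comprehensive assessment of any apparent toxicity experienced by each subject will be performed from the time of giving informed consent up to 12 months", counted from the end of RT.

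**The concern.** A site cannot follow both sets of instructions at the Day 32 visit. Section 7.4.1.2 tells it to record any unfavorable change; Table 7 tells it to record local tolerability only. Section 6.6 tells it to record all medication; Section 7.1.3.7 stops at Day 10.

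Two things are at stake if Table 7 prevails, as is likely because it is the schedule sites work from. First, a systemic event that is not serious and begins after Day 10 falls inside the TEAE definition but is never asked about. The resulting error has one direction: incidence can only be understated. Second, Day 32 blood results are collected without a record of therapy started after Day 10, so a laboratory change cannot readily be sorted into trial treatment or later therapy.

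There is also a drafting gap. The general sections carry 12-month and PTD 365 wording that does not match the 32 days cPoP subjects spend in the trial, so the period over which a site must report adverse events in this part is not stated clearly.

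**Working it through.** **Inputs.** The only M3814 dose and the last RT fraction are on Day 2 (Section 6.3.2). Overall safety is evaluated to Day 10 (Section 5.1). The last visit is Day 32 (Table 7). The TEAE window opens on the day of the first M3814 dose and closes 30 days after the end of RT (Section 7.4.1.3). The Day 10 visit window is ±1 day (Table 7).

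**1. The plan's own figures.** 10 − 2 = 8 and 32 − 2 = 30, matching the 8 and 30 days after treatment given in Section 5.1.

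**2. TEAE window.** Start: Day 2. End: 2 + 30 = Day 32. Length: 32 − 2 + 1 = 31 days.

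**3. Days reached by a systemic adverse event assessment.** Day 2 to Day 10: 10 − 2 + 1 = 9 days. Day 11 to Day 32: 32 − 10 = 22 days not reached. Check: 9 + 22 = 31. Share not reached: 22 / 31 = 71%.

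**4. Sensitivity.** If the Day 10 visit falls on Day 11, 21 / 31 = 68%; if on Day 9, 23 / 31 = 74%. Leaving out the dosing day gives 22 / 30 = 73%. The conclusion does not depend on the counting rule.

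**5. Therapy record.** Other systemic therapy may start after Day 10 and scheduled medication recording stops at Day 10, so the same 22 days have blood results at their end and no scheduled record of therapy within them.

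**6. The 12-month wording.** 2 + 365 = Day 367, and 367 − 32 = 335 days beyond the last scheduled cPoP visit. This measures how far the general text is from the cPoP schedule. It does not count follow-up that was promised and then dropped (see the objection).

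**7. Subjects concerned.** 3 + 3 + 5 = 11 with the capsule, plus about 12 additional, or about 23.

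**The case against.** The strongest reply is that the short follow-up was chosen on purpose and that specific text governs general text. Section 7.1.3.5 expressly leaves cPoP subjects out of long-term follow-up, Section 5.5.2 puts their trial duration at up to 32 days, and Section 5.7 closes this part after 30 days of follow-up. PTD is defined in the Phase Ia and Ib schedules and does not appear in Table 7. This stands. A reader might infer from Sections 7.4 and 7.4.1.3, together with Section 3.6 ("Late toxicities arising 3 months or later after the end of RT can be seen"), that cPoP subjects were owed 12 months of toxicity follow-up and are denied it. The documents do not support that reading; what is missing is a stated exception. Adding long-term contacts would be a separate trade-off. If trial duration were extended with them, they would interact with the rule on joining other trials (Section 5.5.2) and the bar on investigational agents (Section 6.6.2).

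Other parts of the reply also stand. Systemic safety data do not stop at Day 10, because laboratory tests continue to Day 32. Serious events are better protected: SAEs related to M3814 are reportable at any time (Section 7.4.1.3), and SAEs ongoing at the end-of-trial visit are followed until they stabilize or the outcome is known (Section 7.4.1.7). The two irradiated lesions might suggest a within-patient toxicity comparison, but no visible objective or endpoint states one. RT dose need not be equal for the two lesions, and their order is fixed.

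It can also be said that Day 10 is long after a single dose: Section 5.2 gives a half-life of at most 8.8 hours in preliminary data, and 8 × 24 / 8.8 is about 22 half-lives. That may explain the choice, but the TEAE definition rests on time of onset, not on drug exposure.

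Finally, the supplied SAP covers Phase Ia, and its Section 4 defers cPoP to a separate plan, so the cPoP TEAE tables cannot be seen. That limits what can be said about reporting. It does not help with events that were never collected.

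**Conclusion.** The point holds as a conflict between the cPoP schedule and the protocol's own TEAE window. Under Table 7, 22 of 31 window days (71%; 68% to 74% across the Day 10 visit window) have no systemic adverse event assessment, for about 23 subjects. Non-serious systemic TEAEs can be undercounted. The direction is known but the size is not, since the documents give no event rate for those days. Day 32 laboratory results are harder to interpret, though not uninterpretable, because Section 6.6 could still lead some sites to record later therapy.

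This rests on two assumptions: that sites follow Table 7 and Section 7.1.3.7 where these differ from Sections 6.6 and 7.4.1.2, and that Section 8.5.4.1 applies to cPoP, since it names no exception. The primary endpoints in Section 8.3.1 concern Phase Ia and Ib and are not affected. The 12-month and PTD 365 wording is an unreconciled general statement, not evidence that cPoP follow-up was meant to last a year.

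**What to change.** 1. In Table 7, Section 5.1 and Section 7.1.3.7, make the Day 32 adverse event assessment a full one by deleting the restriction to local tolerability. Record concomitant medication and any new anticancer therapy, with start dates, to Day 32. The cost is slightly more data entry at a visit that is already held and at which blood is already drawn. A visit at the early edge of its ±2-day window (Day 30) would still leave two window days unassessed.

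2. In Sections 7.4, 7.4.1.3 and 7.4.1.7, state the cPoP adverse event reporting period explicitly, so that the 12-month and PTD 365 wording agrees with the 32-day participation in Sections 5.5.2, 5.7 and 7.1.3.5. The cost is wording only.

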5.1.1 Dose Escalation Rules

The criteria for dose escalation are based on the occurrence of AEs and/or DLTs that are unrelated to underlying conditions and/or to concomitant medication during the DLT period in evaluable subjects in each cohort. The DLT window of 5 weeks (Phase Ia, Arm A) or 12 weeks (Phase Ia, Arm B and the first 3 subjects in the expansion cohort for Arm A [NSCLC]) after the start of M3814 treatment allows an evaluation of acute toxicity. M3814 dose escalation will not proceed to the next dose level until all subjects in the previous dose level have been observed for the duration of the DLT period. However, RT/CRT and the combination of RT/CRT and M3814 can also give rise to later toxicities. A 3-month mid-term safety follow-up will be performed in all subjects in the Phase Ia part of the trial and, once available, these data will also guide subsequent dose escalation and the establishment of the RP2D. Available PK and PD data will also be taken into consideration.

Dose Escalation During Phase Ia

A Bayesian two-parameter logistic regression model with overdose control will be used to assist the SMC with dose selection during the Phase Ia dose escalation (capsule formulation in Arm A/B, and tablet formulation in Arm B). Cohorts of 3 subjects each will be treated at the same dose level (capsule starting dose: 100 mg QD for Arm A and 50 mg QD for Arm B). The model incorporates prior information (from nonclinical data) and observed information from each completed cohort (and data from all previous cohorts) to provide a recommended dose for the next cohort. A preselected set of acceptable doses are considered by the model, however doses which are not part of the prespecified set may be chosen as well. The model ensures that recommended doses correspond to a probability of less than 25% that the true DLT rate is more than 35% in Arm A and 45% in Arm B. Dose escalation will stop in each arm as soon as the first of the following stopping rules apply: a maximum of 30 subjects are included, more than three cohorts are assigned to the same dose level, or the estimate of DLT probability at the MTD reaches a sufficient precision (see Section 8 for more details).

Selection of the RP2D determined with the capsule formulation will be performed in Phase Ia Arm A based on the available clinical information already generated with the M3814 capsule at escalating doses. Therefore, it is anticipated that a smaller number of dose cohorts and subjects will be required to reassess safety, tolerability and PK of M3814 after dosing with the tablet formulation in combination with RT by use of standard 3+3 dose escalation design criteria (see Section 5.1.2 for more details).

Dose Escalation During Phase Ib

Following completion of the screening and baseline evaluations, treatment-naïve subjects with Stage III A/B NSCLC enrolled in the Phase Ib part of the trial (Arm A expansion cohort) will receive M3814, to be given 1.5 hours (\pm 30 minutes) before each RT fraction for 33 fractions. The dose of M3814 for the first 3 subjects will be established from the available data in both arms of the Phase Ia part of the trial. In case a RP2D in Arm B has been established before a RP2D from Arm A, then the Arm A expansion cohort can be initiated at the RP2D identified in Arm B. In case a RP2D has been established first in Arm A, the first 3 subjects will be treated one dose level below the RP2D. Based on the safety profile, the SMC will decide if the dose can be escalated to the RP2D identified in Phase Ia, Arm A.

The dose in the Arm B expansion cohort will be the determined RP2D of M3814 from Phase Ia Arm B and will be given to subjects with treatment-naïve SCCHN in combination with the same CRT regimen as in Phase Ia (Arm B).

Doses of M3814 in the Ancillary cPoP Part of the Trial

In the ancillary cPoP part of the trial, the doses are fixed at 100 mg, 200 mg, and 400 mg. After the three planned cohorts, additional cohort(s) might be opened upon SMC decision.

The single dose of M3814 to be administered on Day 2 of the ancillary cPoP part of the trial is fixed for successive cohorts as shown in [Table 12](#).

The ancillary cPoP part of the trial will initially be conducted with the capsule; however, additional cohorts of M3814 (CCI formulation) may be introduced. The starting dose and subsequent dose levels of M3814 (CCI formulation) will be defined by the SMC based on PK and safety data generated in ongoing clinical studies evaluating the safety, tolerability, PK, and PD of M3814 (CCI formulation).

Table 12 Doses of M3814 in the Ancillary cPoP Part of the Trial

Dose (mg) ^a	Number of subjects included ^b
100	3
200	3
400	3
(> 100 / < 400) ^c	(3)

cPoP = clinical proof-of-principle; CCI = CCI PK = pharmacokinetics; RP2D = recommended Phase II dose; SMC = Safety Monitoring Committee.

- a. Additional cohorts of M3814 (CCI formulation) may be introduced. The starting dose and subsequent dose levels of M3814 (CCI formulation) will be defined by the SMC based on PK and safety data generated in ongoing clinical studies evaluating the safety, tolerability, PK, and pharmacodynamics of M3814 (CCI formulation).
- b. At the RP2D an additional 2 subjects will be included making 5 subjects at the RP2D.
- c. Additional doses might be opened upon SMC decision.

Dose Interruption and Dose Reduction

Please refer to Section 6.3.1 for detailed information.

All treatment with M3814 will be given in combination with RT; therefore, a delay in RT would lead to a delay in treatment with IMP. See Section 6.6.3.1 for details on handling RT treatment delays.

Definition of Dose Limiting Toxicity

Dose limiting toxicities will be used to determine dose escalation, same dose level extension, and de-escalation and to determine the MTD taking into account the known toxicities with RT alone. DLT is defined in Section 7.4.1.5.

Definition of MTD

The MTD will be defined by the SMC based on the results from all dose escalation cohorts within each arm. See Section 8.1 for details.

Endpoints

Safety will be the primary endpoint for dose escalation in this trial. Other endpoints (PK, PD, efficacy) if available will also be considered. Endpoints are presented in Section 8.3.

Termination of Treatment

Treatment with M3814 will continue until scheduled RT is completed, unacceptable toxicity, withdrawal of consent, or any criterion for withdrawal from IMP occurs (see Section 5.5.1 for criteria). In all cases, when a subject has discontinued all trial treatments for any reason, the Early

Treatment Termination (ETT) visit should be performed. An End of Trial (EOT) visit will be performed on Post-treatment Day (PTD) 365 for those subjects that remain in the trial or in case of premature trial discontinuation prior to PTD Day 365 (see Section 7.1.4).

Withdrawal from the Trial

Subjects will be withdrawn from the trial if they withdraw consent for any further follow-up visits. See Section 5.5.2 for more details.

